## Neurotoxicity

Toxicity Scale for the Sensory Neuropathies Associated with Oxaliplatin Symptoms:

Grade 1	Paresthesias/dysesthesias* of short duration that resolve and do not interfere with function.
Grade 2	Paresthesias/dysesthesias* interfering with function, but not in activities of daily living (ADL)
Grade 3	Paresthesias/dysesthesias* with pain or with functional impairment that also interfere with ADL.
Grade 4	Persistent paresthesias/dysesthesias* that are disabling or life threatening.

\* May be cold induced

For **grade 2 neurotoxicity** persisting between treatments: Do not hold oxaliplatin, but reduce oxaliplatin by one dose level for the next cycle and for all cycles thereafter.

For **grade 3 neurotoxicity** resolving to grade 2 between treatments: Do not hold oxaliplatin, but reduce oxaliplatin by one dose level for the next cycle and for all cycles thereafter.

For **recurrent grade 3 neurotoxicity** resolving to grade 2 between treatments: Do not hold oxaliplatin, but reduce oxaliplatin by one additional dose level for the next cycle and for subsequent cycles. Oxaliplatin will not be reduced beyond level -3. If further dose reduction is required for neurotoxicity, oxaliplatin will be discontinued. Patients should continue to receive other protocol therapy.

For **grade 3 neurotoxicity** persisting between treatments: Discontinue oxaliplatin. Patients should continue to receive other protocol therapy.

For **grade 4 neurotoxicity**: Discontinue oxaliplatin. Patients should continue to receive other protocol therapy.

For **pharyngo-laryngeal dysesthesia**: Increase the duration of oxaliplatin infusion to 6 hours for all subsequent treatments.

### **6.2.2.3 Extravasation**

Extravasation of oxaliplatin has been associated with necrosis; if extravasation is suspected, the infusion should be stopped and the drug administered at another site. Extravasation may be treated according to institutional guidelines.

## **6.2.2 Losartan-related side effects**

### **6.2.2.1 Hypotension**

6.2.1 Patients must demonstrate a systolic blood pressure (SBP) of greater than 100 mm Hg averaged between two resting, seated readings to qualify for study enrollment and will be started at a dose of 25 mg PO qd. They will return for a Day 8 toxicity check at which time BP will be rechecked. If SBP remains greater than or equal to an average of 100 mm Hg on two separate seated checks taken at rest, then the dose will be titrated to 50 mg PO qd. Blood pressure monitoring for study visits or urgent visits relating to hypotension should be used to determine losartan dosing. Blood pressure measurements taken for other reasons do not require losartan dose adjustments or holds. All dose adjustments and modifications are to be made at the discretion of the treating physician.

1. Week 1 Dose reduction (during 25 mg PO qd dosing). BP is not routinely checked. If patients experience lightheadedness or have any other need for vital sign check during D1-8 and SBP is less than an average of 100 mm Hg on two separate seated rested readings, hold Losartan therapy for one week. Patients should have BP recheck at Day 8. If they remain lightheaded or have persistent average SBP <100 mm Hg, they should be unenrolled from the study.

2. Week 2 onward Dose reduction (during 50 mg PO qd dosing for patients who meet criteria for escalation). BP should be checked at each chemotherapy visit and/or if a patient returns for urgent care evaluation or has symptoms of lightheadedness. If average SBP between two separate readings is less than 100 mm Hg, hold Losartan 50 mg PO qd for one week.

3. If Losartan is held, the patient should return one week later for BP recheck. If the patient had specific impetus for hypotension such as infection or dehydration that has resolved, and SBP is greater than an average of 100 mm Hg between two rested, seated readings on recheck, re-initiate Losartan at 25 mg PO qd. In the case where patients are eligible for re-start, patients should return one week later, and if SBP remains greater than an average of 100 mm Hg, the dose should be re-escalate dose to 50 mg PO qd.

4. If Losartan is held in patients at the 50 mg PO qd dose and when they return for recheck, they have sustained low BP (average SBP <100 mmHg), or sustained symptoms of lightheadedness, Losartan should be permanently discontinued and the patient un-enrolled from the clinical trial.

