#### ***Toxicity (Greater than 1%)***

**Hypotension:** Symptomatic first dose hypotension was noted following a 100 mg oral dose, leading to drug discontinuation during a dose finding clinical study (Goldberg et al, 1995b). The incidence appears to be dose-related, increasing from less than 0.5% at doses of 50 mg daily or less, to 2.2% at doses of 100 mg daily (Ellis & Patterson, 1996a).

**Hyperkalemia** Hyperkalemia has been reported during the postmarketing use of losartan (Prod Info Cozaar(R) , 2005). In hypertensive patients with non-diabetic, chronic renal disease, serum potassium was increased significantly to 4.6 mmol/L (mmol/L) from baseline (4.23 mmol/L) during dosing with 100 mg losartan daily, but not with a lower 50 mg daily dose (Gansevoort et al, 1994a). During fixed-dose treatment with losartan 50 mg plus hydrochlorothiazide 12.5 mg in over 200 patients, 11% of patients had changes upward or downward in serum potassium of at least 0.5 mEq/L after 12 weeks (Critchley et al, 1996b). Among 112 hypertensive patients with mild-to-severe renal failure (including 28 on hemodialysis) followed for 12 weeks during losartan treatment, 8% to 18% experienced decreased serum potassium levels greater than 0.5 mEq/L, while 15% to 23% experienced increases greater than 0.5 mEq/L. One patient was withdrawn due to hyperkalemia to greater than 6 mEq/L (Toto et al, 1998).

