#### **6.2.2.2 Hyperkalemia**

For patients with serum potassium registering greater than or equal to 5.0 mmol/L at any time during treatment cycle (i.e. at any lab check), please first verify that the tube was not hemolyzed. If the potassium result is accurate, Losartan at its current dose should be held. Serum potassium should be checked one week later. Treatment may resume at current dose if serum potassium is less than 4.5 mmol/L. If patients have recurrent hyperkalemia after restarting Losartan ( $K >$  or equal to 5.0 mmol/L), the drug should be permanently discontinued and patients will be unenrolled from the study, Treatment of severe hyperkalemia as per routine clinical protocol. All dose adjustments are to be made at the discretion of the treating physician.

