## 9 STUDY CALENDAR

Baseline laboratory evaluations are to be conducted within seven days prior to study entry. Non-laboratory evaluations (imaging, etc) must be done  $\leq 42$  days (6 weeks) prior to study entry. All assessments must be performed prior to administration of any study medication, unless otherwise noted. All study assessments and medications should be

administered within  $\pm$  3 days of the protocol-specified date, unless otherwise noted. All follow up assessments may be performed +/- 21 days of the protocol-specified date.

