## 14 STATISTICAL CONSIDERATIONS

### 14.1 Study Design

14.2 **The single-arm protocol is a phase II study to investigate combining Losartan with FOLFIRINOX for induction chemotherapy followed by restaging and radiation therapy with capecitabine in the treatment of patients with locally advanced pancreatic cancer. The primary endpoint is the rate of R0 (negative margin) resection determined by final pathology of the surgical specimen. Our historical data show a <10% rate of R0 resection among unresectable patients treated with induction chemotherapy followed by chemoradiation. The protocol will have demonstrated an improvement in efficacy if R0 resection were achieved in at least 9 of 50 patients. The decision rule is associated with 91% power if FOLFIRINOX-Losartan with short-course radiation and capecitabine were to improve the R0 resection rate to 25%. In contrast, the probability of a type 1 error is only 6% if the underlying rate of R0 resection were truly the same as the historical level of 10%. All protocol patients who start induction chemotherapy will be included in the denominator for R0 resection analysis, including those who do not undergo surgery due to early progression or other reasons. Sample Size/Accrual Rate** The accrual goal of 50 patients is projected to be enrolled over a total period of 4.5 years. The estimate is based on the overall rate of accrual based on the first 32 patients since the protocol was first open to patient entry. Therefore, we project the enrollment of the remaining 18 patients will require no more than 1.5 years.

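### Section 6.2.2.1 Hypotension, item 1: the week-1 losartan hold lasts one week, but the recheck that can lead to unenrolment is fixed at Day 8, before that week is over for any hold starting after Day 1

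*Combined protocol and SAP*

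**What the plan says.** Section 6.2.2.1 Hypotension (under Losartan-related side effects) has a lead paragraph and four numbered items.

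- **Item 1** covers week 1, on 25 mg daily. If average SBP is below 100 mm Hg at a check prompted during D1-8, the site is to "hold Losartan therapy for one week. Patients should have BP recheck at Day 8". The next sentence reads: "If they remain lightheaded or have persistent average SBP <100 mm Hg, they should be unenrolled from the study".
- **Item 2** covers week 2 onward, on 50 mg, and also orders a one-week hold.
- **Item 3** carries no dose restriction in its opening: "If Losartan is held, the patient should return one week later for BP recheck". If an identifiable cause has cleared and average SBP is above 100 mm Hg, the site is to "re-initiate Losartan at 25 mg PO qd".
- **Item 4** gives the removal rule after a hold, limited to patients on 50 mg.

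Day 8 is a fixed calendar point. Table 1 and section 5.3.5 place it in cycle 1, and the lead paragraph of 6.2.2.1 describes it as a scheduled toxicity check. The other losartan hold rule, 6.2.2.2 Hyperkalemia, times its recheck from the hold: "Serum potassium should be checked one week later". Section 9 allows assessments to move by plus or minus "3 days of the protocol-specified date, unless otherwise noted".

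**The concern.** Item 1 sets the length of the hold relative to when the hold starts, but sets the recheck at a fixed date. The two fit only if the hold starts on Day 1. For any later start, the check that precedes the removal sentence falls before the ordered week off drug has run.

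What is at stake is the date and basis of a removal decision. A patient held on Day 7 and still low or lightheaded on Day 8 could be unenrolled after one day off losartan. Under item 3's timing, the same patient would have a full week off before the check. The interval matters because item 3 itself accepts that low pressure may have a passing cause such as infection or dehydration. Section 2.1.3 describes delayed diarrhea beginning 2 to 4 days after irinotecan and usually lasting 5 to 7 days. An episode in the first cycle could therefore still be active on Day 8, although that section adds that delayed diarrhea often appears after later doses.

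Item 1 also has no restart rule for a week-1 patient who recovers; item 3 is the only hypotension text that has one. A patient held on Day 6 whose pressure is back above 100 mm Hg on Day 8 would literally meet the lead paragraph's condition for going up to 50 mg, in the middle of the ordered hold. Table 1 makes escalation depend on 25 mg having been tolerated in week 1, which should prevent this, but 6.2.2.1 does not say so.

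**Working it through.** **Design figures, for context.** The plan states 91% power and 6% type I error for success at 9 or more R0 resections in 50 patients. Exact binomial calculation reproduces both:

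- P(X ≥ 9 | n = 50, p = 0.10) = 0.0579, which rounds to 6%.
- P(X ≥ 9 | n = 50, p = 0.25) = 0.9084, which rounds to 91%.

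Neither figure depends on the hold rule. Section 14.2 keeps every patient who starts induction chemotherapy in the R0 denominator, so a patient unenrolled under item 1 after starting chemotherapy is still counted.

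**Day arithmetic.** The inputs are:

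- trigger window D1-8, a hold of 7 days and a recheck at Day 8 (6.2.2.1, item 1);
- a window of plus or minus 3 days (section 9), so the latest in-window recheck is Day 8 + 3 = Day 11.

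For a hold starting on Day k:

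- days off drug at Day 8 = 8 − k;
- days off drug at the latest in-window recheck = 11 − k;
- day on which one week off is complete = k + 7;
- delay of that day beyond Day 8 = k − 1.

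| Hold starts (k) | Days off at Day 8 | Days off at Day 11 | Week complete on | Days after Day 8 |
|---|---|---|---|---|
| 1 | 7 | 10 | Day 8 | 0 |
| 2 | 6 | 9 | Day 9 | 1 |
| 3 | 5 | 8 | Day 10 | 2 |
| 4 | 4 | 7 | Day 11 | 3 |
| 5 | 3 | 6 | Day 12 | 4 |
| 6 | 2 | 5 | Day 13 | 5 |
| 7 | 1 | 4 | Day 14 | 6 |
| 8 | 0 | 3 | Day 15 | 7 |

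Only k = 1 reaches 7 days at Day 8. Using the full window, 7 days is reached when 11 − k ≥ 7, that is k ≤ 4. The window therefore rescues starts on Days 2 to 4 and leaves Days 5 to 8 short, at 6, 5, 4 and 3 days. For a hold triggered on Day 8, hold and recheck fall on the same day.

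**Could Day 8 mean day 8 of the hold?** The text does not support this. Item 1 uses D1-8 for cycle days, and section 5.3.5 and the lead paragraph use Day 8 for the scheduled visit.

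**The case against.** The best defence is that Day 8 need not be the decision point. Item 1 does not say in terms that removal is decided on that day. Item 3 applies, on its face, to any hold and brings the patient back after one week. Taken together, Day 8 could be an interim look and the one-week return the deciding one, and item 1's word "persistent" fits that. This reading is possible, so a reader who infers that every such patient must be removed at Day 8 goes further than the documents allow. But item 1 does not say it: the removal sentence follows the Day 8 recheck directly and mentions no later visit. Items 2 to 4 can also be read as the 50 mg pathway only. In that case item 3 does not help, and item 1 still conflicts with itself.

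A second defence is discretion. Section 6 presents its rules as recommendations, item 1 is worded with "should", and sections 5.3.5, 6.2.2.1 and 7.6 leave losartan dosing to the treating physician. This softens the rule in practice. However, those discretion clauses concern dose changes and do not expressly reach unenrolment.

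A third is that little turns on it: the patient is off losartan on Day 8 under either reading, and the trial's operating characteristics do not move. That stands, and it is why the point is minor.

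**Conclusion.** The point holds as a minor internal inconsistency. For holds starting on Days 2 to 8, the recheck attached to the removal rule comes 1 to 7 days before the ordered week is complete. The section 9 window does not cure this for Days 5 to 8. The conclusion rests on reading Day 8 as the cycle 1 visit, which the text supports, and on taking item 1's sentences in sequence, which is the natural reading but not the only possible one.

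Two stronger inferences are not supported:

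- **Effect on the primary result.** A reader might infer that early removals distort it. Power, type I error and the denominator are unchanged.
- **Number of patients affected.** A reader might estimate this from the losartan hypotension incidence in 6.1.8, given as "increasing from less than 0.5% at doses of 50 mg daily or less". That figure follows a sentence on symptomatic first-dose hypotension in a losartan study. It is not a first-week rate of average SBP below 100 mm Hg in patients receiving FOLFIRINOX. The documents give no such rate, so no count can be derived.

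**What to change.** Change item 1 of 6.2.2.1 Hypotension as follows:

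- Place the recheck and the removal decision 7 days after the hold starts. A Day 8 visit that falls within the hold is an interim check only, with neither removal nor escalation.
- State that item 3's restart at 25 mg applies to week-1 holds under item 3's own conditions: the specific cause has resolved and average SBP is above 100 mm Hg.
- Have the investigators state what applies when pressure recovers with no cause identified, since item 3 does not cover that case.

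The cost is a wording amendment and one extra pressure check for some patients. Under the new rule the recheck falls on Days 9 to 15. With 14-day cycles, cycle 2 is planned to start on Day 1 + 14 = Day 15, which is 15 − (k + 7) = 8 − k days after the recheck date. For starts on Days 5 to 8 that gap is 3, 2, 1 or 0 days, within the section 9 window, so the check can be done at the planned visit. An additional visit arises mainly for starts on Days 2 to 4.

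The downside is that the removal decision comes 1 to 7 days later than Day 8. Losartan stays held meanwhile, so the delay adds no exposure to the drug.

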#### **6.2.2.2 Hyperkalemia**

For patients with serum potassium registering greater than or equal to 5.0 mmol/L at any time during treatment cycle (i.e. at any lab check), please first verify that the tube was not hemolyzed. If the potassium result is accurate, Losartan at its current dose should be held. Serum potassium should be checked one week later. Treatment may resume at current dose if serum potassium is less than 4.5 mmol/L. If patients have recurrent hyperkalemia after restarting Losartan ( $K >$  or equal to 5.0 mmol/L), the drug should be permanently discontinued and patients will be unenrolled from the study, Treatment of severe hyperkalemia as per routine clinical protocol. All dose adjustments are to be made at the discretion of the treating physician.

#### **6.2.3 Capecitabine and Radiation**

Hematologic and Non-Hematologic Toxicity

Capecitabine will be held for any Grade 3 or 4 toxicity. After toxicity resolves to  $\leq$  grade 1, capecitabine will be resumed at 600 mg/m^2 BID to complete the 10 weekdays of therapy.

Capecitabine can be held a maximum of 7 days. If further grade 3 or 4 toxicity is noted at the

reduced dose level, after toxicity resolves to  $\leq$  grade 1, capecitabine will be resumed at 500 mg/m^2 BID to complete two weeks of therapy. If the second dose reduction is not tolerated, capecitabine will be stopped. Patients will keep a capecitabine diary and will record the number of capecitabine tablets and the time that they take the tablets.

Radiation therapy will be held for Grade 3 or 4 nausea that is not well controlled with antiemetic support, until nausea resolves to Grade 2 or less. It will then be resumed at same dose.

Grade 3 or 4 toxicities that are due to biliary ductal dilatation and resolved with placement of a biliary stent or with biliary stent change will not require a dose reduction of capecitabine or radiation therapy after stent placement. Therapy may be withheld for procedures like ERCP and biliary stenting, and restarted at the treating physician's discretion.

## **7 DRUG FORMULATION AND ADMINISTRATION**

### **7.1 5-Fluorouracil (5-FU; fluorouracil; Adrucil" )**

Please refer to the package insert for complete product information.

#### *Availability*

5-FU is commercially available as a 50 mg/mL solution for injection in 10 mL, 20 mL, 50 mL and 100 mL vials.

#### *Preparation*

Inspect for precipitate; if found, agitate or gently heat in water bath. Bolus injections are prepared using undiluted drug. 46-48 hour infusion of 5-FU should be prepared for administration via ambulatory infusion pump according to the individual institution's standards. These solutions may be prepared in D5W or 0.9% NaCl. 5-FU should not be mixed in the same solution with most parenteral antiemetics.

#### *Storage and Stability*

Intact vials should be stored at room temperature and protected from light. Slight yellow discolor does not usually indicate decomposition. Stability in ambulatory pumps varies according to the

pump, manufacturer of drug, concentration and diluent. Please refer to appropriate reference sources for additional information.

#### *Administration*

In this study, 5-FU is administered as a 400 mg/m^2 IV bolus followed by 2400 mg/m^2 by IV infusion over 46 to 48 hours.

#### *Drug Interactions*

Leucovorin enhances the cytotoxicity of 5-FU by forming a more stable tertiary complex with thymidylate synthase. Concomitant administration of 5-FU with warfarin has been reported to result in increased INR/prolonged prothrombin time. Patients receiving both drugs should be followed with weekly INRs.

### **7.2 Leucovorin Calcium (Folinic Acid) Leucovorin Calcium (calcium folinate; citrovorumfactor; N 5-formyltetrahydrofolate; 5-formyl-FH4; folinic acid).**

Please refer to the package insert for complete product information.

#### *Availability*

Leucovorin calcium is commercially available in: 50 mg, 100 mg, 350 mg vials for reconstitution.

#### *Storage and Stability*

Intact vials should be stored at room temperature and protected from light. Solutions reconstituted with BWI are stable for at least 7 days at room temperature.

#### *Preparation*

Leucovorin may be reconstituted with Bacteriostatic Water for Injection (BWI) or with Sterile Water For Injection. Solutions should be further diluted in D5W, 0.9% NaCl or Rungers solution for infusion over two hours.

#### *Administration*

Leucovorin will be administered as a 400 mg/m^2 IV infusion over 2 hours +/- 10 minutes after oxaliplatin/irinotecan administration. Leucovorin may also be administered concurrently with oxaliplatin/irinotecan as a separate IV infusion.

### **7.3 Oxaliplatin [Eloxatin]**

#### *Availability*

Oxaliplatin is commercially available as an aqueous solution in vials containing 50 mg and 100 mg at a concentration of 5 mg/mL. The vials do not contain any preservative and they are intended for single use. Oxaliplatin is commercially available.

#### *Storage and Stability*

Intact vials should be stored at room temperature. Solutions diluted in D5W are stable for 6 hours at room temperature or 24 hours under refrigeration.

#### *Preparation*

The calculated dose of oxaliplatin should be diluted for infusion with 250 mL to 500 mL D5W. Oxaliplatin should not be diluted with a sodium chloride solution. Needles, syringes, catheters or IV administration sets containing aluminum should not be used with oxaliplatin. As with other platinum compounds, contact with aluminum may result in a black precipitate.

#### *Administration*

Oxaliplatin will be administered by intravenous infusion over 120 minutes +/- 10 minutes. Infusion time may be prolonged (up to 6 hours) in patients experiencing pharyngolaryngeal dysesthesia. Oxaliplatin is unstable in the presence of chloride or alkaline solutions. Do NOT mix or administer oxaliplatin with saline or other chloride-containing solutions. Do NOT administer other drugs or solutions in the same infusion line. Flush IV lines/catheters with Dextrose 5% in Water both before and after oxaliplatin administration.

### **7.4 Irinotecan (CPT-11, CAMPTOSAR®)**

#### *Availability*

Irinotecan is commercially available as a 20 mg/mL solution for injection in 2 mL and 5 mL vials.

#### *Storage and Stability*

Intact vials should be stored at controlled room temperature 59° to 86° F (15° to 30° C) and when protected from light. Solutions diluted in D5W are reported to be stable for 48 hours under refrigeration and protected from light. Irinotecan solutions should not be frozen as the drug may precipitate.

### *Preparation*

Irinotecan is diluted in 5% dextrose (D5W) 500 mL to a final concentration of 0.12 – 1.1 mg/mL.

### *Administration*

In this study irinotecan will be administered as an IV infusion over 90 minutes +/- 10 minutes.

